3.3.2 VB-111

Dose modifications of VB-111 are not allowed.

VB-111 will be permanently discontinued for:

- Any grade 2 VB-111 related adverse event that has not resolved to grade 1 within 2 weeks or requires systemic treatment.
- Any grade 3 non-skin VB-111 related adverse events that has not resolve to grade 2 within 7 days.
- Any grade 4 VB-111 related adverse event.

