Cytokine and angiogenic biomarker response showed considerable variability in cytokine/cytokine receptor levels. An approximately 100-fold increase in IL-6 occurred at 6 hours post-dosing, correlating with the fever that occurred at the same time. This elevation was transient, returning to pre-infusion levels by day 4. Results also showed transient but smaller increases in IL-8, sTNFR-1, and sTNFR-2 levels at the 6-hour post-dosing time point. There was no suggestion of a cytokine storm.

Based on above findings the VB-111 dosing interval of Q56 days was chosen. A shorter dosing interval of 28 days was assessed in study VB-111-122 in patients with recurrent glioblastoma (GBM). However, interpretation of the results of this cohort were inconclusive due to its small sample size (10 patients) and the concomitant administration of bevacizumab. However, we believe that every 6-week dosing is feasible based on the kinetics of VB-111. As mentioned, by approximately 1 month, a significant amount of VB-111 expression has been lost.

Additional bio-distribution data are available for 24 subjects, of which, 6 subjects received multiple doses of VB-111. Findings demonstrate that patients have a uniform peak level of adenovirus DNA of approximately 10^7 copies/ μ g and, there was no attenuation of peak levels with repeat dosing. All patients had rapid clearance of DNA levels within a few hours, with a drop of at least 3 logs or more. Some patients retained basal levels between doses, while in others the levels between doses dropped to zero.

Based on the results from the phase I trial, VB-111 was advanced into tumor specific, repeat dose trials including:

- A Phase 1/2 clinical trial in ovarian cancer (VB-111-157), which combined VB-111 therapy with the chemotherapeutic agent paclitaxel.
 - The population of the study included Patients ≥ 18 years of age with progressive recurrent platinum resistant or refractory ovarian cancer including epithelial ovarian, peritoneal or fallopian tube cancers.
 - Twenty-one patients at two US centers received up to seven repeat doses of VB-111 in combination with weekly paclitaxel, and 17/21 received the therapeutic VB-111 dose. Median age was 65 (41-79) with a median of 3 prior lines of therapy.
 - No new toxicities nor DLTs were observed. VB-111 was associated with expected flu-like symptoms and mild infusion reactions and the drug was safe and well tolerated.

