2.1.2 Exclusion Criteria

- Patients who have had standard-of-care anti-cancer therapy or therapy with investigational agents (e.g. chemotherapy, immunotherapy, endocrine therapy, targeted therapy, biologic therapy, tumor embolization, monoclonal antibodies or other investigation agents), large field radiotherapy, or major surgery within 4 weeks prior to enrollment.
- Patients who have had anti-VEGF therapy within 4 weeks prior to enrollment.
- Patients currently on a corticosteroid dose greater than physiologic replacement dosing defined as 10 mg of cortisone per day or its equivalent.
- Patients with known brain metastases because of their poor prognosis and because they often develop progressive neurologic dysfunction that would confound the evaluation of neurologic and other adverse events.
- Patients with signs of liver failure, e.g. clinically significant ascites, encephalopathy, or variceal bleeding within 6 months prior to enrollment.

- Prior major liver resection: remnant liver <50% of the initial liver volume. Patients with a biliary stent can be included.
- Patients with active autoimmune disease or history of autoimmune disease that might recur, which may affect vital organ function or require immune suppressive treatment including systemic corticosteroids. These include but are not limited to patients with a history of immune related neurologic disease, multiple sclerosis, autoimmune (demyelinating) neuropathy, Guillain-Barre syndrome or CIDP, myasthenia gravis; systemic autoimmune disease such as SLE, connective tissue diseases, scleroderma, inflammatory bowel disease (IBD), Crohn's, ulcerative colitis, hepatitis; and patients with a history of toxic epidermal necrolysis (TEN), Stevens-Johnson syndrome, or phospholipid syndrome. Such diseases should be excluded because of the risk of recurrence or exacerbation of disease.
 - Of note, patients with vitiligo, endocrine deficiencies including thyroiditis managed with replacement hormones including physiologic corticosteroids are eligible. Patients with rheumatoid arthritis and other arthropathies, Sjogren's syndrome and psoriasis controlled with topical medication and patients with positive serology, such as antinuclear antibodies (ANA), anti-thyroid antibodies should be evaluated for the presence of target organ involvement and potential need for systemic treatment but should otherwise be eligible.

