3.2 DRUG ADMINISTRATION

3.2.1 VB-111 Administration

VB-111 will be given on Day 1 of cycle 1 and continue every 3 cycles (cycles 4, 7, 10 and so on) at a flat dose of 1x10¹³ or 0.7x10¹³ VP.

VB-11 should be fully administered within 60 minutes (±30 minutes) after dilution in room temperature 0.9% sodium chloride solution.

Acetaminophen 500-1000 mg will be administered orally 30 minutes-2 hours prior to VB-111 infusion and followed by 325-500 mg as needed every 4-6 hours post treatment up to 36 hours. In patients who develop > grade 3 fever following VB-111 administration or at the discretion of the investigator, dexamethasone IV 10 mg may be administered 20 minutes to 3 hours prior to treatment (but no sooner than 20 minutes) in subsequent VB-111 doses.

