4 CONCOMITANT MEDICATIONS/MEASURES

All routine and appropriate supportive care (including blood products) will be provided during this study, as clinically indicated, and in accordance with the standard of care practices. Clinical judgment should be utilized in the treatment of any AE experienced by the patient.

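### Sections 3.2.1 and 3.3.2 are not reconciled for VB-111 related fever, either on whether as-needed acetaminophen triggers the grade 2 discontinuation limb or on what follows a grade 4 fever

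*Combined protocol and SAP*

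**What the plan says.** Section 3.3.2 allows no VB-111 dose modification and lists three grounds for permanent discontinuation:

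- Grade 2: "Any grade 2 VB-111 related adverse event that has not resolved to grade 1 within 2 weeks or requires systemic treatment".
- Grade 3: "Any grade 3 non-skin VB-111 related adverse events that has not resolve to grade 2 within 7 days".
- Grade 4: "Any grade 4 VB-111 related adverse event".

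Section 3.2.1 gives oral acetaminophen before each VB-111 infusion, "followed by 325-500 mg as needed every 4-6 hours post treatment up to 36 hours". It then addresses higher-grade fever: "In patients who develop > grade 3 fever following VB-111 administration or at the discretion of the investigator, dexamethasone IV 10 mg" may be given before later VB-111 doses.

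Section 1.2.5.6 describes the timing of fever in the phase I study: "An approximately 100-fold increase in IL-6 occurred at 6 hours post-dosing, correlating with the fever that occurred at the same time". Section 1.2.5.7 names pyrexia first among the reactions most commonly associated with VB-111. Section 4 states: "All routine and appropriate supportive care (including blood products) will be provided during this study, as clinically indicated".

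**The concern.** Fever is the most predictable reaction to VB-111, so the rule for permanent discontinuation should be clear for it. Two things are unclear.

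First, the two conditions in the grade 2 limb are joined by an or, so needing systemic treatment is enough without any delay in resolution. The term is not defined, and no exception is written for drugs that the protocol itself provides. The grade 3 limb has a time test and no treatment condition. On its wording, the rule can therefore be stricter for the milder event.

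Second, Section 3.2.1 looks ahead to later VB-111 doses after a fever that Section 3.3.2 treats as ending VB-111, if it is grade 4 and related.

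What is at stake is consistent conduct of a safety rule. Two investigators could handle the same fever in opposite ways, and each could cite the protocol. Departures from the protocol are logged under Section 8.8, and safety and tolerability are a primary objective. Section 6.1 does not collect grade 1 events, so the unclear limb applies at the lowest grade recorded. Section 1.2.6 also cites a fever response that correlated with survival as support for an immune effect. That association comes from earlier trials. It shows that fever matters to the rationale, not that fever brings benefit.

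**Working it through.** The plan states no figure on this point, so the check is mainly a comparison of text.

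**1. Can the grade 2 limb be reached?** The fever is reported at 6 hours after dosing (Section 1.2.5.6), and as-needed acetaminophen runs to 36 hours (Section 3.2.1). Since 6 < 36, the fever falls inside the window. The drug is oral, hence systemic in the ordinary sense. If a related grade 2 fever needs it, the literal condition can be met.

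**2. The two sections by course of a related fever:**

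| Course | Section 3.2.1 | Section 3.3.2 |
|---|---|---|
| Grade 2, needs acetaminophen | Acetaminophen provided | Permanent stop if this counts as required systemic treatment; otherwise no stop, if it settles in time |
| Grade 3, treated, directly to grade 1 or below within 7 days | Premedication at later doses possible | No limb met |
| Grade 3, treated, to grade 2 within 7 days and still treated | Premedication at later doses possible | Grade 3 limb not met; whether the grade 2 limb then applies is not stated |
| Grade 3, not down to grade 2 in 7 days | Premedication at later doses possible | Permanent stop |
| Grade 4 | Premedication at later doses provided for | Permanent stop |

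The literal rule is stricter for the milder event when the first row is compared with the second. For the third row the text does not settle it.

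**3. The symbol before grade 3 in Section 3.2.1.** It may be a misprint or an extraction loss for ≥. Other thresholds differ in the same way: >10 mm in Section 6.2.1 against ≥ 10 mm in Section 6.2.2 for calipers, and > 35kg in Table 5 against ≥ 35kg in the Section 3.5 footnote. Under > the provision starts at grade 4; under ≥ it starts at grade 3. Grade 4 is covered either way, so the mismatch with the grade 4 limb does not depend on the symbol. It does depend on the fever being judged VB-111 related, because Section 3.2.1 speaks of fever following administration and Section 3.3.2 of related events.

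**4. How many patients?** The documents give any-grade fever only:

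- Section 1.2.5.1, glioblastoma study: 25/46 = 54.3%.
- Section 1.2.5.7, ovarian study with paclitaxel: 9/20 = 45.0%.

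If these rates carried over to 24 evaluable patients (an assumption), fever of any grade would be expected in 24 × 0.450 = 10.8 to 24 × 0.543 = 13.0 patients. The share that is grade 2, related and needing treatment is not given. With that share anywhere from 0% to 100%, the expected count runs from 0 to 10.8 or 13.0. That is not an estimate.

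**5. Effect per affected patient.** With 14-day cycles and VB-111 at cycles 1, 4 and 7, doses fall on days 1, 43 and 85. The first scan at 8 weeks is nominally day 57. A stop after dose 1 leaves 1 of the 2 doses planned before that scan, as any early VB-111 stop would.

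**6. Design figures.** The two-stage rule in Section 10.2 (9 then 24 patients, 0/9 stops, 3 or more of 24 is of interest) uses no input from this rule. Its early-termination probability is 0.95^9 = 0.630, matching the stated 63.0%.

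**The case against.** The best defence is that the sections can be read together. Acetaminophen in Section 3.2.1 is part of the administration procedure, and taking a drug as needed is not the same as an event requiring systemic treatment. Section 2.1.2 uses the term in contrast to topical medication, within a criterion about immune suppression, where patients "should be evaluated for the presence of target organ involvement and potential need for systemic treatment". Routine supportive care is provided under Section 4 without any statement that giving it ends a study drug. On dexamethasone, Section 3.2.1 is permissive: Section 3.3.2 decides whether VB-111 continues, and Section 3.2.1 says what may be given if it does. Finally, if VB-111 stops for toxicity, Section 3.1 lets nivolumab continue at the investigator's discretion, and Section 10.3 keeps a patient with one dose of each agent in the efficacy evaluation.

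Much of this stands. The trigger is possible, not certain, and a narrower meaning is plausible. But that meaning is not written in Section 3.3.2. Where the protocol means steroids or immunosuppressants, it names them (the nivolumab table in Section 3.3.1, and Section 4.1). The Section 4 argument rests on silence. The permissive reading of the dexamethasone sentence softens the grade 4 mismatch but leaves a provision for later doses in a case where, for a related fever, none may follow.

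A reader might also infer that patients with grade 3 fever continue while those with grade 2 fever are stopped. The documents do not establish that in general. The limbs are not stated to be exclusive, so a grade 3 fever that has fallen to grade 2 and is still treated might meet the grade 2 limb as well.

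**Conclusion.** The point holds as a failure to reconcile two sections, and it should be fixed. Section 3.3.2 leaves open whether protocol-provided acetaminophen meets the systemic-treatment condition, and how its limbs apply when one event changes grade. Section 3.2.1 provides for premedicated later doses after a range of fever that includes grade 4, against a permanent stop for related grade 4 events.

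Its size in patients is unknown. This conclusion rests on the literal wording, on the fever being judged VB-111 related and, for the grade 2 part, on acetaminophen being needed rather than merely taken.

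Three stronger readings are not supported. The documents do not show that every treated grade 2 fever must end VB-111. They do not show that a material share of patients would lose VB-111, because no grade split is given. Nor do they show harm to the design's error rates, since no Section 10.2 figure depends on this rule. Section 3.3.2 is a per-patient discontinuation rule, distinct from the study stopping rules in Section 3.4.

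**What to change.** The sponsor's clinicians should reconcile Sections 3.2.1 and 3.3.2 by:

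- stating in Section 3.3.2 whether antipyretic use provided under Section 3.2.1 counts as required systemic treatment;
- stating how the grade 2 and grade 3 limbs apply to a single event that changes grade;
- checking the fever-grade symbol in Section 3.2.1 against the source document, and aligning that sentence with the grade 4 limb.

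Which clinical rule to adopt is for them to decide, and none is suggested here. Outcomes may still depend on time to resolution or on the investigator's judgement, as long as both sections say the same thing. The cost is a short amendment to two sections, with no added visits or patients and no change to the sample size.

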3.4 STUDY STOPPING RULES

For safety reasons, the enrollment will be temporarily halted until an expedited safety report is sent to and reviewed by the FDA and the SAE has been evaluated by the investigators for either of the following events attributable to treatment regimen occurring within 30 days of receiving investigational agent:

- One occurrence of grade 5 toxicity
- Two occurrences of grade 4 toxicity

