3 STUDY IMPLEMENTATION

3.1 STUDY DESIGN

The proposed study is an open label, single-arm phase II study of VB-111 in combination with anti-PD1, nivolumab, in patients with advanced, refractory CRC.

Treatment will be delivered in cycles consisting of 2 weeks (+/- 3 days).

VB-111 will be administered every 6 weeks starting on cycle 1 day 1 and nivolumab will be administered every 2 weeks starting on cycle 2 day 1 ([Schema 1](#) and [Table 5](#)).

[figure not shown]
Treatment will continue until off treatment criteria are met (see Section [3.7.1](#))

If one of the study drugs is permanently discontinued because of toxicity, the patient may continue the other study drug per PI discretion until off treatment criteria are met (Section [3.7.1](#)).

Patients will be monitored every 8 (+/- 1) weeks with imaging.

Treatment will be delivered without planned hospitalization. Admission for logistical reasons is allowed (i.e. if patients cannot travel home the same day or biopsies are scheduled etc.)

Patients will have two mandatory research biopsies: at baseline and either day 1 of cycle 2 (post VB-111 but pre-checkpoint inhibitor treatment) or day 1 of cycle 4 (post-VB-111 and checkpoint inhibitor treatments). Timing of the research biopsy will be determined in an alternating fashion by the research team on a 1:1 basis; i.e. the team will assign patient #1 to early second biopsy (day 1 of cycle 2), patient #2 to late second biopsy (day 1 of cycle 4) and so on.

Schema 1: Study design. Patients will undergo pre-treatment biopsy and one post-treatment biopsy at Day 1 of Cycle 2 or Day 1 of Cycle 4.

Table 5: Treatment regimen

VB-111, every 6 weeks	Nivolumab, every 2 weeks
1x10 ¹³ VP IV (for patients with weight ≥ 50kg)	240 mg IV
0.7x10 ¹³ VP IV (for patients with weight > 35kg and <50 kg)	

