8.1.5 Relationship to Study Product

All AEs will have their relationship to study product assessed using the terms: related or not related.

- Related – There is a reasonable possibility that the study product caused the adverse event. Reasonable possibility means that there is evidence to suggest a causal relationship between the study product and the adverse event.
- Not Related – There is not a reasonable possibility that the administration of the study product caused the event.

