12.4.1.1 Risk of biopsy

All care will be taken to minimize risks that may be incurred by tumor sampling. However, there are procedure-related risks (such as bleeding, infection and visceral injury) that will be explained fully during informed consent.

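### The enrollment-halt rule in section 3.4 does not cover a death, or two grade 4 complications, attributed solely to the mandatory research biopsies

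*Combined protocol and SAP*

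**What the plan says.** Section 3.4 of the protocol pauses enrollment, pending FDA review of an expedited safety report and evaluation by the investigators, for "either of the following events attributable to treatment regimen occurring within 30 days of receiving investigational agent". Two thresholds follow: "One occurrence of grade 5 toxicity" and "Two occurrences of grade 4 toxicity".

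The table in section 3.1 titled "Table 5: Treatment regimen" has two columns, VB-111 and nivolumab. The biopsies are set out in the same section, outside that table: "Patients will have two mandatory research biopsies: at baseline and either day 1 of cycle 2" or day 1 of cycle 4. Section 2.4 places the baseline biopsy in the 28 days before the first dose. Section 5.1 says the liver is the site in more than 90% of cases. On sampling, section 12.4.1.1 states that "there are procedure-related risks (such as bleeding, infection and visceral injury"), and gives no rate.

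On causality, section 8.1.5 says: "All AEs will have their relationship to study product assessed using the terms: related or not related". It has no category for a study procedure. Section 6.1 starts adverse event documentation at day 1 of cycle 1, and section 8.2 starts SAE reporting to the sponsor at the first administration of investigational product.

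**The concern.** The trial exposes patients to two kinds of research risk: the drugs, and a required invasive procedure done twice. Within this protocol the biopsies serve an exploratory objective, the adenovector level in tumor. The automatic halt protects later patients from the first kind of risk only. If a patient died of a complication put down entirely to the biopsy, the rule as written would let the next patient be enrolled and undergo the same required procedure with no pause. The same holds after two grade 4 biopsy complications. At stake is the reach of a trial-level safety rule; no error rate or sample size depends on it.

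**Working it through.** The plan gives no figure on this point, so the check is textual, with some counting.

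**1. Does the rule reach a biopsy event?** Section 3.4 needs attribution to the treatment regimen. Table 5 defines that regimen as the two drugs, and no section adds the biopsy. Section 8.1.5 offers only related or not related to study product, where related means a reasonable possibility that the product caused the event. Three cases follow:

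| Event | Reasonable possibility of drug cause | Solely due to biopsy |
|---|---|---|
| One grade 5 | Counts (if in window): halt | Not counted: no halt |
| Two grade 4 | Count (if in window): halt | Not counted: no halt |
| One grade 4 | No halt | No halt |

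The attribution limit therefore decides the outcome in the first two rows only.

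**2. Does the 30-day window matter too?** Cycles last 14 days, plus or minus 3. VB-111 is given on day 1 of cycles 1, 4, 7 and so on, and nivolumab on day 1 of each cycle from cycle 2.

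- *Baseline biopsy:* no agent has been given. It falls outside the window as well as outside the attribution test.
- *Cycle 2 day 1:* 14 days after VB-111 (range 11 to 17). Inside the window.
- *Cycle 4 day 1:* 14 days after the cycle 3 nivolumab dose (range 11 to 17), but 3 × 14 = 42 days after the last VB-111 dose (range 3 × 11 = 33 to 3 × 17 = 51).

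The last case depends on what section 3.4 means by investigational agent. The title page lists VB-111 as the investigational agent and nivolumab as commercial. If the term covers VB-111 only, a complication of a cycle 4 biopsy that arises before that day's VB-111 dose is outside the window, even at the shortest permitted spacing (33 days). The protocol does not fix the order of biopsy and dose on that day. If the term covers both drugs, the event is inside.

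**3. How many procedures are affected?** At the accrual ceiling of 27 in section 10.2, 27 × 2 = 54 biopsies. If the trial stops after 9 evaluable patients, those 9 account for 9 × 2 = 18. Both are maxima, because section 5.1 leaves the second biopsy to discretion after early progression.

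- By attribution: a complication due solely to the biopsy is uncounted for all 54.
- By timing, if both drugs count as investigational agents: the 27 baseline biopsies are also outside the window.
- By timing, if only VB-111 counts: alternating assignment starting with the early slot gives 14 early and 13 late second biopsies among 27 patients, so up to 27 + 13 = 40 are outside, on the pre-dose assumption above.

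**4. Does another section require a pause?**

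- 7.3: non-progression deaths within 30 days of a research intervention are emailed to the Clinical Director within one business day. Reporting only.
- 7.4.1 and 8.7: reports to the biosafety committee and FDA turn on association with VB-111 or causality with study product.
- 7.5.1 and 7.5.2: the research team meets about weekly, and the safety monitoring committee reviews about annually. Neither is tied to a halt.
- 13.1: suspension for significant or unacceptable risk is permitted, not required.

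None of these makes a pause mandatory.

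**The case against.** The strongest reply is that the protocol already has adequate responses. Section 13.1 lets the study be suspended, section 7.3 brings a death to the Clinical Director quickly, the team meets about weekly, section 5.1 has interventional radiology judge the biopsy safe before enrollment, and coagulation tests are repeated each cycle. Section 8.2 also collects an alternate etiology for events judged unrelated, so a biopsy cause would be recorded once adverse event collection has begun. All of that stands. It means a biopsy death would not go unnoticed, but it does not supply the automatic pause that section 3.4 gives for a drug death.

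Four stronger readings are tempting, and the documents do not support them.

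- *That any life-threatening biopsy complication escapes a halt it would otherwise trigger.* A single grade 4 event does not halt enrollment even when it is drug-related.
- *That a bleed caused jointly by VB-111 and the biopsy would be missed.* Section 8.1.5 asks only for a reasonable possibility of drug causation, so such an event already counts. Nothing in the documents shows that it would tend to be put down to the biopsy.
- *That Table 4 shows a raised risk of biopsy bleeding.* Elevated PTT, wound dehiscence and every hemorrhage entry are in its uncommon column, cerebral hemorrhage was seen only in glioblastoma studies, and no hepatic or procedural bleeding is listed.
- *That a probability can be attached to the gap.* No complication rate is given. Pooling grades 4 and 5 into a chance of at least one event would also not match a rule that needs one grade 5 or two grade 4.

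The objection that the remedy is more than a single added clause is also right, and the fix allows for it.

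**Conclusion.** The point holds in a limited form. One death, or two grade 4 complications, attributed solely to the mandatory research biopsies triggers no automatic enrollment halt. This applies to as many as 54 procedures. The 27 baseline biopsies are excluded on timing as well, and some cycle 4 biopsies may be too if investigational agent means VB-111 alone. The conclusion rests on reading treatment regimen as Table 5 presents it and on the investigator judging that there is no reasonable possibility of drug causation. It does not say that the protocol is silent on such an event, since discretionary suspension and death reporting remain. How often the gap would matter cannot be estimated from the documents. The change is worth making because the procedure is required of every patient and its serious risks are acknowledged.

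**What to change.** Four linked edits are needed.

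1. **Section 3.4:** apply the existing thresholds (one grade 5, two grade 4) also to events attributable to a protocol-mandated research biopsy, timed from the biopsy date and including the baseline biopsy. State which body's review lifts such a halt, because the present condition is FDA review of an expedited safety report, and section 8.7 ties such reports to causality with the product. Say whether investigational agent includes nivolumab.
2. **Section 6.1:** start recording biopsy-related adverse events at the baseline biopsy.
3. **Section 8.2:** extend SAE reporting to biopsy events before the first dose. Without items 2 and 3, a baseline event would not be captured for the amended rule to act on.
4. **Section 8.1.5:** add relationship to research biopsy as a separate causality item. Section 6.1 already plans separate fields for VB-111 and nivolumab, so this is one more field. The alternate-etiology entry in 8.2 is collected only when an event is judged unrelated to product.

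The cost is small edits to four sections, one extra case report form field, and a possible short enrollment pause after a serious biopsy complication. Sample size, error rates and the two-stage response rule do not change.
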